4. STUDY DESIGN AND CLINICAL PROCEDURES

This is an open-label, dose-escalation study to examine the safety, tolerability, dose, and PK of VRC01.23LS in healthy adults as shown in the study schema (Table 2).

Table 2: VRC 615 Study Schema

VRC 615 Study Schema						
Group	Subjects	VRC01.23LS Dose and Route	Dosing Schedule			
			Day 0	Week 12	Week 24	
1	3	5 mg/kg IV	X			
2	3	5 mg/kg SC	X			
3	3	20 mg/kg IV	X			
4	3	40 mg/kg IV	X			
5	5	5 mg/kg SC	X	X	X	
6	5	20 mg/kg IV	X	X	X	
Total	22*	*Enrollment up to a total of 40 subjects is permitted if additional subjects are necessary for safety or PK evaluations.				

The study will be conducted at a single site, the Vaccine Evaluation Clinic located at the NIH Clinical Center (NIH CC).

Enrollment will begin with the 5 mg/kg dose groups (Groups 1, 2 and 5) with no more than one subject per day at the 5 mg/kg dose for the first 3 subjects. Enrollments into the subsequent dose groups (Groups 3, 4, and 6) will proceed after dose-escalation reviews as described in [4.4](#).

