4.3.1.2. Compensation

Subjects will be compensated for time and inconvenience in accordance with the standards for compensation of the NIH CC Clinical Research Volunteer Program. Compensation for a study visit that includes IV product administration is \$430; a study visit that includes SC product administration is \$375. If enrollment occurs on a different day than study product administration, then visit compensation will be \$85. Compensation will be \$200 for scheduled follow-up visits that include venipuncture, \$85 for clinic visits that do not include venipuncture, and \$25 for timely completion of all 7 days of the electronic diary card. The total amount of compensation varies depending upon the group and the visits completed.

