4.3.3. Enrollment, Study Days and Visit Numbers

In this study, enrollment is defined as the assignment of a study identification number and study group schedule in the clinical database. A clinician will discuss the target dates and timing of the study product administration(s) and sample collections before completing an enrollment to help ensure that the subject can comply with the projected schedule. Informed consent must be obtained prior to enrollment.

Day 0 is defined as the day of first VRC01.23LS administration. Day 0 may occur on the same day as enrollment or up to 6 weeks after enrollment. This period may be increased with PI approval. If Day 0 does not coincide with enrollment, then the enrollment day may be referred to by a negative number of days (i.e., Day -1 to Day -42). For calculating elapsed days following Day 0, each subsequent calendar date is labeled by the next sequential “Study Day” as shown in the Schedule of Evaluations ([Appendix I](#)). Since there may be more than one research sampling timepoint of interest per study day, each sample collection timepoint has its own “Visit Number.” For this reason, there may be more than one visit number recorded on the same calendar date.

Medical history and Day 0 evaluations prior to the first study product administration are the baseline for subsequent safety assessments.

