8.2. Risk/Benefit Assessment

8.2.1. Potential Risks

Risks of VRC01.23LS and mAb Administration

The side effects of mAbs are mild but may include reactions at the injection site (pain, redness, bruising, swelling), fever, chills, rigors, nausea, vomiting, pain, headache, dizziness, shortness of breath, bronchospasm, hypotension, hypertension, pruritus, rash, urticaria, angioedema, diarrhea, tachycardia or chest pain. Clinical use of mAbs that are targeted to cytokines or antigens associated with human cells may be associated with an increased risk of infections [\[41\]](#); however, this is not expected to be a risk for a mAb targeted to a viral antigen.

Administration of mAbs may cause immune reactions such as acute anaphylaxis, serum sickness, and the generation of antibodies. However, these reactions are rare and more often associated with mAb targeted to human proteins or with the use of murine monoclonal antibodies which would have a risk of human anti-mouse antibodies [\[41\]](#). It is expected that that VRC01.23LS

will have a low risk of such side effects since it is directed against a viral antigen and is human in origin.

Published experience with other human mAb directed against cell surface targets on lymphocytes have shown that infusion of a mAb may be associated with cytokine release, causing a reaction known as “cytokine release syndrome” (CRS) [42]. Most infusion-related events occur within the first 24 hours after beginning administration. Severe reactions, such as anaphylaxis, angioedema, bronchospasm, hypotension and hypoxia, are infrequent and more often associated with mAbs targeted to human proteins or when a non-human mAb, such as a murine mAb, is used [41]. Specifically, with regard to the rare CRS reactions, these generally occur within the first few hours of beginning the infusion and are more common with the first mAb infusion received. This is because the cytokine release is associated with lysis of the cells targeted by the mAb and the burden of target cells is greatest at the time of the first mAb treatment. With licensed therapeutic mAbs, CRS is managed by temporarily stopping the infusion, administration of histamine blockers, and restarting the infusion at a slower rate [43].

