8.2.2 Assessment of Potential Risks and Benefits

The potential risks associated with participation of healthy volunteers in this study and receiving VRC01.23LS has been informed by results of previous VRC trials evaluating similar HIV mAbs with a favorable safety profile, as described in [1.2](#) and in the IB. In addition, a protocol specific risk management plan with a risk register has been established for this trial and assesses potential risks and strategies to mitigate risk, such as gradual initial enrollment in each dose group with a dose escalation plan ([4.4](#)) and study pause ([4.5](#)) and product discontinuation criteria ([4.6](#)) to minimize risk to subjects.

There are no direct benefits to study subjects from study participation. However, the study may benefit others as there is a potential benefit from knowledge gained in this study that would further inform the clinical development of HIV mAbs for the prevention or treatment of HIV infection.

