¹Day 0=day of first product administration. Day 0 is preferably scheduled within 14 days after enrollment but may be scheduled up to 42 days after enrollment to allow for the possibility of study pauses or scheduling difficulty with the approval of the PI. Day 0 evaluations prior to product administration are the baseline for assessing subsequent AEs.

(Footnotes continue to next page)

² Screening includes physical exam with vital signs (blood pressure, temperature, pulse, respiratory rate), height and weight. At other visits, if medically indicated, perform a targeted exam. Otherwise only vital signs are required, except at Visit 02 when the current weight is also obtained to use for ordering the study product, dosed based on “mg/kg.”

³ The PK blood draw “visits,” defined by hours after an infusion, are relative to the exact time of the end of infusion (EOI). The exact start and end times of product administration and the time of PK blood draw(s) are recorded to ensure accurate PK analysis. In all IV groups, subjects will be observed in clinic for at least 2 hours following completion of product administration.

⁴ Pregnancy test results must be negative for women of reproductive potential before each product administration. Complete a Pregnancy Prevention Form when pregnancy test is given.

Schedule 2: SC Group 2 (5 mg/kg)																
Visit Number	01	01R	02	02A	02E	02F	02G	03	04	05	06	07	08	11	12	13
Time After Infusion			Pre	EOI	24hr	48hr	72hr	Wk1	Wk2	Wk3	Wk4	Wk8	Wk12	Wk16	Wk20	Wk24
¹ Day of Study	-56 to -1	-42 to 0	D0	D0	D1	D2	D3	D7	D14	D21	D28	D56	D84	D112	D140	D168
Clinical	Tube*	Screen	Enroll	Day of Injection												
VRC 500 Screening Consent		X														
VRC 615 AoU; Consent			X													
² Physical examination		X	X	X	X	X	X	X	X	X	X	X	X	X	X	X
Complete medical history at screen; then interim med hx		X	X	X		X	X	X	X	X	X	X	X	X	X	X
³ VRC01.23LS Administration				X												
Begin 7-day Diary Card				X												
CBC / differential	EDTA	3		3		3			3	3		3		3		
ALT, creatinine	GLT	4		4		4			4	4		4		4		
CMP: Total bili, BUN, albumin, protein, calcium, Na, K, Cl, CO ₂ , glucose, AST, ALP	GLT	X		X						X						
⁴ Pregnancy test: urine or serum		X	X	X						X				X		X
⁴ Pregnancy Prevention Counseling		X	X	X						X				X		X
HIV Ab/Ag combo test	EDTA	3							3							
HIV Risk-Reduction Counseling		X		X					X							
Research Samples																
PK	SST			4		4	4	4	4	4	4	4	4	4	4	4
PBMCs	EDTA			20		20										
Serum	SST			24			8	8	8	8	8	8	8	8	8	8

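### The one-subject-per-day limit for the first three subjects at 5 mg/kg is tied to enrollment, not to first administration, so first-in-human doses may fall on the same day

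*Combined protocol and SAP*

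**What the plan says.** The spacing rule is in Section 4, below the study schema: "Enrollment will begin with the 5 mg/kg dose groups (Groups 1, 2 and 5) with no more than one subject per day". The limit in full reads "with no more than one subject per day at the 5 mg/kg dose for the first 3 subjects", so it covers the first three subjects pooled over Groups 1 (IV), 2 (SC) and 5 (SC, repeat dosing).

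Section 4.3.3 makes enrollment a defined term: "enrollment is defined as the assignment of a study identification number and study group schedule in the clinical database". It defines Day 0 separately, as the day of the first administration, and sets the allowed lag: "Day 0 may occur on the same day as enrollment or up to 6 weeks after enrollment". The PI may extend that period. Footnote 1 to the schedules in Appendix I adds a preference: "Day 0 is preferably scheduled within 14 days after enrollment but may be scheduled up to 42 days after enrollment". It gives study pauses and scheduling difficulty as the reasons for the longer lag, with PI approval.

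Enrollment on its own day is a planned case. Section 4.3.1.2 sets a payment that applies as follows: "If enrollment occurs on a different day than study product administration". Appendix I gives enrollment its own visit (01R, Day -42 to 0).

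Section 8.2.2 counts the following among the measures that reduce risk: "gradual initial enrollment in each dose group with a dose escalation plan".

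**The concern.** This is the first trial of VRC01.23LS in humans. Early doses are spaced so that an acute reaction in one subject can be seen before the next is exposed. Section 8.2.1 gives the relevant time scale: "Most infusion-related events occur within the first 24 hours after beginning administration". Observation in the clinic is at least 2 hours after IV dosing and at least 1 hour after SC dosing (Section 4.3.5), and nothing requires it to be complete before another subject is dosed.

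The sponsor chose a calendar-day stagger, but the text attaches it to a database step. The safeguard can be met on paper while two or three first doses are given on one day, and that would not breach the rule as worded. A study pause shows how this could arise. If the first recipient triggered one, the second and third subjects might already be enrolled. When dosing resumed, the enrollment limit would not stop both being dosed on the same day.

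**Working it through.** The plan states no figure for the interval between first doses, so there is none to reproduce. The check compares the event that the rule limits with the dates on which dosing is then allowed.

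**Inputs**
- Limit: at most one enrollment per day for the first three subjects at 5 mg/kg (Section 4).
- Lag from enrollment to Day 0: 0 to 42 days allowed (Section 4.3.3), 14 days or fewer preferred (Appendix I, footnote 1).

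**Step 1: a compliant schedule.** Enroll one subject on each of days 1, 2 and 3. The rule is met. Give all three their first dose on day 3.

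| Subject | Enrolled | Day 0 | Lag (days) |
|---|---|---|---|
| 1 | day 1 | day 3 | 3 − 1 = 2 |
| 2 | day 2 | day 3 | 3 − 2 = 1 |
| 3 | day 3 | day 3 | 3 − 3 = 0 |

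The largest lag is 2 days, inside both the 14-day preference and the 42-day allowance. The gap between first doses is 0 days.

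**Step 2: how many dates allow this.** A subject enrolled on day e may be dosed on any day from e to e + w. For enrollments on days 1, 2 and 3, all three windows overlap from day 3 to day 1 + w, which is w − 1 dates. At least two overlap from day 2 to day 2 + w, which is w + 1 dates.

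| Window w | Dates open to all three | Dates open to at least two |
|---|---|---|
| 14 days (preferred) | days 3 to 15: 13 | days 2 to 16: 15 |
| 42 days (allowed) | days 3 to 43: 41 | days 2 to 44: 43 |

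The overlap does not depend on the long 42-day lag; the preferred window is enough.

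**Step 3: the limit on Day 0 instead.** The same subjects are dosed on days 3, 4 and 5, each with a lag of 2 days. The smallest gap is 1 calendar day. The number of dates on which two or three may share a first dose falls to 0. The last dose moves by 5 − 3 = 2 days.

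**Step 4: does another section supply the spacing?**
- Sections 4.3.4 and 4.3.5 (administration, observation) set no daily cap and no interval between recipients.
- Section 4.4 (escalation reviews) governs moves between IV dose levels, using data through Day 7. It does not space doses within 5 mg/kg, and it states that the SC groups do not wait for those reviews.
- Section 4.7 (pausing) acts only after events have occurred.
- Section 8.2.2 is also worded on enrollment and gives no daily limit.
- Section 8.9 (safety monitoring) provides for review of data, not for timing of doses.

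**The case against.** The best reply is that the rule means dosing. Its sentence has already named the 5 mg/kg groups, so repeating the dose adds little unless the limit is on subjects receiving it. Section 8.2.2 treats gradual enrollment as protection, which makes sense only if it spaces exposure. This is good evidence of intent, but it does not settle the text. The repeated words can equally name the dose level being enrolled, and enrollment has its own definition in this protocol.

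Other points bear on consequence. There is one site, an advanced clinician is available during dosing and observation (Section 4.3), and a Safety Officer reviews data daily (Section 8.9). The statement about 24 hours comes from a discussion of cytokine release with antibodies against cell-surface targets. Section 8.2.1 expects low risk here because the target is viral and the antibody is human in origin. Sections 1.3.1 and 1.3.2 report no related SAEs with the parent antibodies, and 5 mg/kg is the lowest dose. All of this stands and lowers the likely harm, but none of it spaces exposure.

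A calendar-day limit also does not guarantee 24 hours, since a late dose may be followed by an early one the next morning. That is true, but the proposed change is only meant to secure the stagger that the sponsor already chose.

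Finally, the risk management plan cited in Section 8.2.2 and the operating procedures cited in Section 8.9 are not in these documents and may already set spacing. That possibility stands.

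**Conclusion.** The concern holds. As written, the minimum gap between the first three first-in-human doses is 0 calendar days; with the limit on Day 0 it is 1 calendar day. The conclusion rests on the protocol's own definition of enrollment, on a literal reading of the sentence in Section 4, and on the absence of any other dosing limit in these documents. It does not claim that same-day dosing is planned, and dosing each subject on the day of enrollment would satisfy either reading. No endpoint or analysis is affected. The change should be made because a stated first-in-human safeguard can otherwise be met without doing its work. Confidence is medium, given the probable intent and the operational documents not seen.

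**What to change.** In Section 4, tie the limit to exposure: for the first three subjects at 5 mg/kg, across Groups 1, 2 and 5, no more than one subject per day receives a first VRC01.23LS administration (Day 0).

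The cost is one sentence of protocol wording and slightly less freedom in scheduling. If the risk management plan already spaces doses, the edit brings the protocol into line with it.

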4.4. Criteria for Dose-Escalation

This study will include a series of interim safety reviews to assess product safety in a stepwise manner. The activation of additional dose groups will proceed in a staged manner that is governed by the outcome of the planned interim PSRT data reviews. The PSRT must assess the data as showing no significant safety concerns before proceeding with group activation.

Table 3: Plan for Dose-Escalation Reviews

Data Review Objective	Minimum Evaluable Safety Data*	Favorable Review Outcome
Review #1		
• Dose-escalation from 5 to 20 mg/kg IV	• All post-administration safety data from Day 0 through at least the “Day 7” visit in at least 3 5-mg/kg IV recipients from Group 1.	• Proceed with enrollment into Groups 3 and 6.
Review #2		
• Dose-escalation from 20 to 40 mg/kg IV	• All post-administration safety data from Day 0 through at least the “Day 7” visit in at least 3 20 mg/kg IV recipients from Groups 3 or 6.	• Proceed with enrollment into Group 4.

Group 2 and Group 5 enrollment (5 mg/kg SC) does not depend on dose-escalation reviews for the IV doses.

If there are discontinuations from the study before there are sufficient data to conduct the dose-escalation review, then additional subjects may be enrolled to have the requisite data on at least 3 subjects at the dose level and route being evaluated. Additionally, AEs assessed as related to the study product at the time of a dose-escalation review may be judged by the PSRT to warrant adding additional subjects to a particular group. Consultation with the IRB or FDA as per study pause criteria may occur if indicated.

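### Section 8.2.2 relies on gradual entry in each dose group, but the only pacing rule covers the first 3 enrollments at 5 mg/kg and none at 20 or 40 mg/kg

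*Combined protocol and SAP*

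**What the plan says.** Section 8.2.2 describes how risk to healthy volunteers is contained. It refers to a separate risk management plan and gives examples of mitigation, "such as gradual initial enrollment in each dose group with a dose escalation plan", with a pointer to Section 4.4.

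Section 4 starts enrollment with Groups 1, 2 and 5, all at 5 mg/kg, under the limit "no more than one subject per day at the 5 mg/kg dose for the first 3 subjects". For the higher doses it says only: "Enrollments into the subsequent dose groups (Groups 3, 4, and 6) will proceed after dose-escalation reviews".

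Section 4.4 (Table 3) sets two reviews, each needing data through at least the Day 7 visit in at least 3 IV recipients at the preceding dose. A favorable Review #1 leads to "Proceed with enrollment into Groups 3 and 6". A favorable Review #2 opens Group 4.

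Section 4.3.3 defines enrollment as the assignment of a study number and group schedule in the database. It adds: "Day 0 may occur on the same day as enrollment or up to 6 weeks after enrollment". The PI may extend that interval.

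**The concern.** The risk assessment credits the plan with gradual entry in every dose group, but the operating sections provide it only for the first few subjects at the lowest dose. Sections 4.3.4, 6.2, 6.2.1 and 8.9 and the schedules in Appendix I contain no other stagger or sentinel rule.

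This is the first human use of the antibody. Section 8.2.1 says: "Most infusion-related events occur within the first 24 hours after beginning administration". Section 4.3.5 requires at least 2 hours of clinic observation after an infusion. If several subjects receive a first dose at a new level on one day, a reaction that appears that evening or the next morning cannot inform the decision to dose the others.

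The pause rule in Section 4.7 does not fill this gap. It needs one related SAE, or the same related Grade 3 or higher event in two subjects, with self-limited Grade 3 events that resolve in the solicited period left out. A single non-serious reaction does not trigger it, and a pause protects only subjects who have not yet been dosed.

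**Working it through.** This is mainly a comparison of texts, with counts from Table 2.

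**Planned total.** Four groups of 3 and two groups of 5: 4 × 3 + 2 × 5 = 22, which matches Table 2.

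**Subjects by dose level and route**

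| Level | Groups | Planned | Covered by the Section 4 pacing rule |
|---|---|---|---|
| 5 mg/kg IV | 1 | 3 | 3 in total over both routes |
| 5 mg/kg SC | 2, 5 | 3 + 5 = 8 | (same 3) |
| 20 mg/kg IV | 3, 6 | 3 + 5 = 8 | 0 |
| 40 mg/kg IV | 4 | 3 | 0 |
| All | 1–6 | 22 | 3 |

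**Coverage now.** 3 / 22 = 13.6%. At the two higher doses, 8 + 3 = 11 of 22 planned subjects have no pacing inside their level. After Review #1, all 8 planned subjects at 20 mg/kg could be enrolled on one day without a protocol deviation. After Review #2, so could all 3 at 40 mg/kg.

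**Route.** At 5 mg/kg, 8 of 3 + 3 + 5 = 11 places are SC. The 3 paced subjects are counted over all three groups, so none of them need be an IV recipient.

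**Enrollment against dosing.** The Section 4 limit is written for enrollment. Under Section 4.3.3, three subjects enrolled on three different days may each have Day 0 up to 6 weeks later, so all three may have the same Day 0. Read literally, the rule does not stagger exposure even where it applies.

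**Between levels against within a level.** The Section 4.4 reviews decide when a dose level opens. They say nothing about how quickly subjects enter it afterwards. Section 8.2.2 names gradual entry in each group together with the escalation plan, so the reviews alone do not deliver what it describes.

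**Coverage under the fix.** Four dose-route levels × 3 subjects = 12 of 22. Pacing by dose level alone, with routes pooled, would give 3 × 3 = 9 of 22.

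**Clinic days added**, assuming subjects would otherwise be dosed as fast as the current text allows:
- 20 mg/kg: 3 − 1 = 2
- 40 mg/kg: 3 − 1 = 2
- 5 mg/kg: at most 6 − 3 = 3, if the two routes never share a day

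Total: at most 2 + 2 + 3 = 7.

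**The case against.** The sponsor could answer that Section 8.2.2 is summary text that loosely combines the staged opening of dose groups with the Section 4 rule. The same sentence cites Section 4.5 for study pauses, although the pause criteria are in Section 4.7. The sentence is also about a separate risk management plan, which may contain a pacing rule. The daily limit at 5 mg/kg is naturally read as a limit on dosing. Appendix I prefers Day 0 within 14 days of enrollment and keeps the longer interval for pauses or scheduling difficulty.

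On safety, nobody receives 20 or 40 mg/kg until at least 3 recipients of the preceding IV dose have been reviewed, and Review #1 requires Group 1 IV recipients specifically. After a first IV dose, visits are scheduled up to 4 hours and again at 24 and 48 hours. Section 8.2.1 says the rare cytokine release reactions generally appear within the first few hours. No related SAEs are reported for VRC01 or VRC01LS, and the tissue study found no specific membrane binding.

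Much of this stands. Expected risk is low, the review between IV levels is real protection, and the clinic may well stagger in practice. The SC-only possibility matters less because Review #1 needs IV data.

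None of it supplies a pacing rule at 20 or 40 mg/kg, however. A rule in a plan outside the protocol is not a protocol requirement. The later visits monitor subjects already dosed. A preferred 14-day window still allows same-day first doses. Reading the 5 mg/kg limit as one on dosing, or as one for each 5 mg/kg group, leaves the higher levels uncovered.

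**Conclusion.** The concern holds. Section 8.2.2 claims a protection that the protocol's own rules give to 3 of 22 planned subjects, all at 5 mg/kg, and to none of the 11 planned at 20 and 40 mg/kg. Where the rule does apply, it restricts enrollment and not first dosing.

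The counts use the planned sizes in Table 2. The protocol permits up to 40 subjects, and any added at the higher doses would also be unpaced. The conclusion rests on the protocol text alone, because the risk management plan is not among the documents. It makes no estimate of the probability of harm. With low expected risk, infusions that can be slowed or stopped, an advanced clinician in the clinic and daily safety review, this is a modest safety correction that should be made.

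**What to change.** In Section 4 or 4.4, state that no more than one subject per day receives a first dose of VRC01.23LS for the first 3 subjects at each dose level and route: 5 mg/kg IV, 5 mg/kg SC, 20 mg/kg IV (Groups 3 and 6 counted together) and 40 mg/kg IV. Tie the limit to Day 0, not to enrollment. Keep the present pooled limit for the first 3 subjects at 5 mg/kg, also expressed as first doses.

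The cost is a change of wording in one section and at most 7 clinic days. Sample size and analysis are unaffected.

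If the sponsor decides against pacing at the higher doses, amend Section 8.2.2 so that it claims pacing only for the first 3 subjects at 5 mg/kg. That removes the inconsistency at no operational cost but adds no protection. In either case, correct that sentence's reference for study pauses from Section 4.5 to Section 4.7.
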